4.5 Other health outcomes

4.5.1 Pandemic and pre-pandemic periods

- Pre-pandemic period will be considered from January 1st 2018 to March 14th 2020
- Pandemic period will be considered from March 14th 2020 to the end of study period

4.5.2 Severity

Both hospitalizations and stays in ICU will be considered for severity analyses

4.6 Covariates

Covariate information will be collected on sociodemographic, spatial information, vaccination against Sars-Cov-2 and comorbidities. The source of the eHR databases and the variables needed to create the covariates is given in Annex 1.

4.6.1 Sociodemographic variables

Age

Age will be treated as time-dependent variable. Population follow-up will be stratified according to the following four age groups (18-49/50-64/70-79/≥80).

Sex

Female/Male

Rural residence

Rural residence (yes/no) will be classified based on the law for sustainable development of the rural environment from the Regional Government. Rural areas are classified according to population density (<100 inhabitants/km2), urban nucleus proximity, population trend, percentage of employment in primary, secondary and tertiary sectors and territorial structure.

Nationality

Spanish/Other

Social exclusion risk

At risk (yes/no). The classification is based on multiple aspects including unemployment, foreigner in irregular situation or without resources.

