4.9.2 HZ incidence rates estimations

Data from a previous study from our team (28), using the same health databases from Valencia Region showed an incidence rate of HZ of 5.02 (4.99–5.04), 5.3 (5.3-5.4), 7.3 (7.2-7.4), 8.3 (8.2-8.4) and 8.6 (8.5-8.8) per 1000 persons-year in subjects \geq 18, 50-59, 60-69, 70-79 and \geq 80 years old, respectively.

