4.9.6 Primary objective

To develop the primary objective, we will compare the incidence of HZ among SARS-Cov-2 free and Sars-Cov-2 laboratory-confirmed subjects 50 years and older during the pandemic period. For this purpose, models using individual patient data or grouped will be implemented.

[figure not shown]

Figure 4: Cohort diagram for HZ rates comparison among subjects with and without previous episode of COVID19

The risk of HZ in subjects with Sars-cov-2 respect to subjects without Sars-Cov-2 will be estimated by a multivariate Poisson or negative binomial model according to applicability assumptions. Individual data will be grouped by SARS-Cov-2 free and Sars-Cov-2 laboratory-confirmed exposure, age, sex and comorbidities. Individual and grouped data can both be analyzed with the Poisson (or Negative binomial) distribution. Given the usual large size of the cohort, estimation when using grouped data is considerably quicker than when using individual level data and the results for both approaches are remarkably similar.

The number of HZ cases by aggregation unit will be compared among SARS-Cov-2 free and labconfirmed subjects. Age, sex, and comorbidities will be considered for the adjustment, and the person-time-at-risk (in years) as an offset term. RR and their 95% confidence or credible intervals will be reported.

Besides, individual-level risk of HZ between SARS-Cov-2 free vs lab-confirmed will be estimated by Cox regression model for right censored data. The abovementioned variables will be also considered for the adjustment.

Both approaches will be performed and compared for the robustness of the results.

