4.9.9 Secondary objectives

- 1) A statistical analysis like the previous one will be developed to compare the risk of HZ among individuals 18 years and older between SARS-CoV2-free and lab-confirmed.
- 2) The risk of HZ in subjects with Sars-Cov-2 exposed (pandemic) respect to subjects unexposed (pre-pandemic) will be estimated by a multivariate Poisson or negative binomial model according to applicability assumptions. Age, sex and comorbidities will be considered for the adjustment.

3) Describe the likelihood of developing HZ after laboratory-confirmation of SARS-CoV2 according to severity of disease.

We will calculate and compare the predicted probability of developing incident HZ in the 1, 3, 6 months following Sars-Cov-2 (1, 3, 6 – months cumulative incidence) using logistic

regression models. We will compare the overall probability, regarding Sars-Cov-2 severity, and the probabilities obtained from models adjusting for the abovementioned covariates (See section 3.5).

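### The protocol's only definition of age is four wide groups (with 65-69 in none), too coarse for adjustment given its own herpes zoster rates by age

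*Protocol*

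**What the plan says.** Section 4.6.1 (Age) contains the only definition of the age covariate: "Age will be treated as time-dependent variable", followed by "Population follow-up will be stratified according to the following four age groups", which are 18-49, 50-64, 70-79 and 80 and over. The list moves from 64 straight to 70.

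The analysis sections use age without giving it any other form:

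- Section 4.9.6, grouped Poisson or negative binomial model: "Individual data will be grouped by SARS-Cov-2 free and Sars-Cov-2 laboratory-confirmed exposure, age, sex and comorbidities". For the regression: "Age, sex, and comorbidities will be considered for the adjustment". The Cox model reuses the same variables.
- Section 4.9.9, first secondary objective: a similar analysis to "compare the risk of HZ among individuals 18 years and older between SARS-CoV2-free and lab-confirmed".
- Section 4.9.9, severity: logistic models compare unadjusted probabilities with "the probabilities obtained from models adjusting for the abovementioned covariates". The cross-reference given there is to a section 3.5, which the document does not contain.

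Section 4.9.2 gives earlier HZ rates from the same databases for ages 50-59, 60-69, 70-79 and 80 and over: "5.3 (5.3-5.4), 7.3 (7.2-7.4), 8.3 (8.2-8.4) and 8.6 (8.5-8.8) per 1000 persons-year". The rate for all adults is 5.02. No rate is given for any group below 50. Annex 1 lists date of birth among the extracted variables.

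**The concern.** A model that carries age as these four groups treats everyone inside a group as having the same background HZ risk. If the compared subjects differ in mean age inside a group, that difference passes into the rate ratio as if it were an effect of infection or of severity. The 50-64 group lies across the steepest rise that the protocol documents and belongs to the primary population. The 18-49 group spans 32 single years of age.

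The study is sized to detect a rate ratio of 1.1 (section 4.9.5), so a residual of a few percent is not negligible. A gradient by severity is where age is the most obvious competing explanation. Filling the 65-69 gap alone would not help, because 18-49 and 50-64 would remain wide. If the gap were closed by reading the second group as 50-69, that group would contain the whole documented step.

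**Working it through.** **Plan's own figure.** The protocol states no figure for residual age confounding. Its one design figure, power 0.760864 for a rate ratio of 1.1, is reproduced closely: 0.759 with a two-sided Poisson score test at one person-year per subject. It is not in dispute and serves here only as a yardstick.

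**1. Documented age gradient (section 4.9.2).** Annual rise = (later rate / earlier rate)^(1/10) − 1.

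- Fifties to sixties: 7.3/5.3 = 1.377, so 1.377^0.1 − 1 = 3.25% per year (log slope ln(1.377)/10 = 0.0320).
- Sixties to seventies: (8.3/7.3)^0.1 − 1 = 1.29% per year.
- Seventies to 80 and over: (8.6/8.3)^0.1 − 1 = 0.36%, or 0.30% if the midpoints are 12 years apart.

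**2. Residual inside a group.** For slope g and mean age difference d, the spurious ratio is (1+g)^d.

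- 50-64, g = 3.25%: 1.03, 1.07 and 1.10 for d = 1, 2 and 3 years.
- 70-79, g = 1.29%: 1.01, 1.03 and 1.04.
- 80 and over, g = 0.36%: at most 1.01 for 3 years.

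A residual of 1-3% in the primary ratio corresponds to d of about 0.3 to 0.9 years at the steepest slope (ln 1.01/ln 1.0325 = 0.31; ln 1.03/ln 1.0325 = 0.92). That d is an assumption.

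**3. Implied rate at 18-49.** Let s be the share of adult person-time at 50 and over and m the mean rate there, both assumed. The rate below 50 is (5.02 − s·m)/(1 − s). The slope to the fifties, over 20.5 years between midpoints, is (5.3/rate)^(1/20.5) − 1.

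| s | m | Rate 18-49 | Slope per year |
|---|---|---|---|
| 0.40 | 6.5 | 4.03 | 1.3% |
| 0.50 | 7.0 | 3.04 | 2.7% |
| 0.55 | 7.2 | 2.36 | 4.0% |

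**4. 18-and-over comparison, inside 18-49.** Section 4.9.3 gives positives of 40,880 (20-29), 42,441 (30-39) and 52,776 (40-49), which are 30%, 31% and 39%, with mean age about 35.4. The age mix of infection-free subjects is not given, so shares are assumed. The ratio is the mean of (1+g)^age in positives divided by that in free subjects, with decade midpoints 24.5, 34.5 and 44.5.

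- Free subjects 24/31/45%: 0.98 at g = 2%, 0.96 at 3.25%.
- Equal thirds: 1.02 and 1.03.
- Free subjects 36/33/31%: 1.03 and 1.05 (1.045).

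The range is about 0.96 to 1.05, and the sign depends on the assumed mix.

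**5. Severity comparison.** The protocol gives no ages by severity. If hospitalised cases in 18-49 average 3, 5, 8 or 10 years older, (1+g)^d is 1.06, 1.10, 1.17 and 1.22 at 2%, and 1.10, 1.17, 1.29 and 1.38 at 3.25%.

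**6. How large can d be?** Suppose ages are uniform over width W and hospitalisation risk rises as exp(k·age). The shift in mean age is W/(1 − e^(−kW)) − 1/k − W/2.

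- W = 15 (50-64): 1 year needs a 2.2-fold rise across the group; 3 years needs about 20% per year (14-fold); 6 years needs a near doubling each year (over 20,000-fold).
- W = 32 (18-49): 3 years needs about 3.7% per year (3.2-fold); 5 years needs about 6.4% per year (7.4-fold).

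Gaps of several years are therefore feasible at 18-49 but not at 50-64.

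**The case against.** The strongest objection is that no analysis section says age enters the models in these groups only. Section 4.6.1 speaks of stratifying follow-up, section 4.9.6 allows individual as well as grouped data, and the coding of a covariate is commonly settled in a statistical analysis plan, which is not at hand. A reader might infer that the protocol commits every model to four age groups; the text does not go that far. What stands is narrower. These groups are the only form of age defined, they are placed in the covariate section, and a grouped model needs age categories. An analyst following the protocol has no others to use.

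A reader might also apply the 3% slope to the 32-year group. It is documented for one step, fifties to sixties. Below 50 the protocol gives no rate, and a slope of 1.3-4.0% per year is inference from assumed shares.

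Third, a reader might assume hospitalised cases 3-6 years older within a group and conclude that the severity ratio is inflated by 10-21%. At 50-64, where the slope is documented, gaps of that size need implausibly steep hospitalisation risk. At 18-49 such gaps are feasible, but the slope is not documented.

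Finally, adjustment for comorbidities may absorb part of the age effect, and the severity objective is worded as descriptive. Both points reduce the weight of the problem without removing it.

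**Conclusion.** The point holds as a weakness in the one age definition that the protocol gives, not as an error in any stated result. The gap at 65-69 is a plain defect of the list and reaches the primary population. The width of 50-64 conflicts with the protocol's own evidence of a 38% rise between the fifties and the sixties.

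The likely effects, all resting on assumed age differences, are:

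- **Primary 50-and-over ratio:** probably 1-3%, based on about 3% per year of in-group age difference at 50-64 and less at older ages.
- **18-and-over ratio:** about 0.96 to 1.05 from the 18-49 group, sign unknown.
- **Severity comparison:** possibly larger, mainly at 18-49, if hospitalised cases are several years older within that group. The protocol has no data to establish this.

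The main and 18-and-over residuals are below the target ratio of 1.1. The case for change is that the weakness is avoidable with data already requested.

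**What to change.** In section 4.6.1, correct the list so that ages 65-69 are covered, and state that the wide groups serve descriptive tables only. In sections 4.9.6 and 4.9.9, state that every model adjusts for attained age calculated from date of birth:

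- in 5-year bands for the grouped Poisson or negative binomial models;
- as a spline for the individual-level Poisson, Cox and severity logistic models.

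Replace the pointer to section 3.5 with the section that defines the covariates.

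The cost is more grouping cells and slightly more analysis work. Section 4.9.1 expects about 4 million eligible subjects, which can support the extra cells. No new data are needed.

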4.6.2 Spatial variables

The spatial variables are summarized in Figure 2:

Figure 2. Geographical stratification of the Valencia Region health care system: Province, Health Department, Health Care District and Municipality.

4.6.3 Comorbidities

Comorbidities that have been identified as risk indicators for HZ will be considered for the analysis. These conditions will be identified by systematic search of ICD-codes in the hospital or ambulatory databases, MBDS or SIA. Subjects will be considered to

Disease classification	ICD-10
Diabetes	E10-E14
COPD	J44
Ischemic heart disease	120-125
Other heart disease	127-152
Kidney disease	N18-N19
Immunocompromised	
HIV	B20-B24
Cancer	C00-D49
TOTS	Z94
IBD	K50-K51
RA	M05-M14
SLE	M32

have a given condition from the first appearance of the comorbidity-related diagnosis date until the end of the follow-up period.

COPD: chronic obstructive pulmonary disease, HIV: human immunodeficiency virus, TOTS: Transplanted organ and tissue status, IBD: inflammatory bowel disease, RA: rheumatoid arthritis, SLE: systemic lupus erythematous.

Presence of any comorbidity.

This is a binary variable indicating whether the patient has at least one comorbidity defined above.

Number of underlying conditions

This is a categorical variable indicating the number of comorbidities (0, 1, 2, 3+).

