4.2 Study population and period

The cohort will include all subjects older than 18 years living in Valencia Region, registered in the Regional Health System (RHS) (over 98%) from January 1st 2018 to, at least, December 31st 2020 (or date of data extraction). The inclusion and exclusion criteria will be the following:

Inclusion criteria: Subjects aged 18 years and above covered by the RHS and residing in the Valencia Region during study period.

Exclusion criteria:

- Subjects with less than 12 months of registration to the RHS and subjects with incorrect codification.
- Subjects vaccinated against HZ before the diagnosis of SARS-CoV-2
- Subjects vaccinated against SARS-CoV-2 before the diagnosis of SARS-CoV-2

Start of follow-up: The start of the follow-up is defined as the latest of start of the study (1st January 2018), first date of registration in the database or date of the 18th birthday.

End of follow-up: The end of the follow-up is defined as the earliest of the following cases:

- End of study period
- Loss of follow-up (exit of RHS)
- Exitus
- Vaccination with HZ vaccine
- Vaccination with COVID-19 vaccine
- Development of HZ

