4.8 Data collection

The following variables (Annex 1) will be requested to the different databases for the period from July 2017 until at least December 31st 2020 (depending on the date of data extraction) for subject's \geq 18 years. Data privacy will be protected by using dissociated data.

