3.1. LIST OF VARIABLES TO BE EXTRACTED FROM DATABASES

Data privacy will be protected by using anonymised data (see 2.2. section). The following variables will be requested to the different databases for the period from 1 January 2007 to 31 January 2015 for subjects \geq 18 years old:

Data to be extracted from SIP:

- Identification block including SIP number, sex, date of birth and other geographical of birth, place and date of registration (excluding identifying data as surnames, ID card number, phone numbers, etc.)
- Assignation block (including municipality, healthcare district, etc)
- Regular location block that includes complete address, health map information as health department and census information among others (excluding exact data that allows the exact residence location of the subjects)
- Cessation block including cessation cause and description, cessation date and date of death (when applicable)
- APSI code
- Barthel Index

Data to be extracted from SIA

- SIP number

Morbidity database

- Date of diagnosis activation (diagnosis of interest)
- Date of diagnosis deactivation (diagnosis of interest)
- Diagnosis description (diagnosis of interest)
- ICD-codes (diagnosis of interest)

Outpatient visits database

- Date of the visit
- Diagnosis description
- ICD-code

Specialist visits database

- Date of the visit
- Diagnosis description
- ICD-code
- Professional attendance (GP/Specialist)
- Specialist service

For any diagnosed code related to HZ (see section 4.3) and comorbidities (see section 4.6.3)

Data to be extracted from MBDS:

- Anonymized Personal Identification Number (SIP)
- Birth date
- Sex
- Municipality of residence
- Postal code
- Health department
- Health care district
- Date of hospital admission
- Date of hospital discharge
- Diagnoses at discharge (main and secondary diagnoses)
- Procedures during the hospitalization
- Discharge destination (destination on discharge)
- ICU (any position)
- POA

For any diagnosed code related to HZ (see section 4.3) and comorbidities (see section 4.6.3) and SARS-Cov-2 (J12.89, J20.8, J40, J22, J98.8, J80, R65.20, R65.21, R05, R06.02, R50.9, R43.0, Z20.828, Z03.818, Z11.59 O98.5, B97.29 or U07.1 and B34.2)

Data to be extracted from RedMIVA

- SIP number
- Date of laboratory test (dd/mm/yyyy)
- Date of test result
- Sample type
- Laboratory test (PCR, antigen, etc)
- Result

For any SARS-Cov-2 test

Source	Dataset	Variable	Label	Туре	Coding

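### Unless diagnoses from before July 2017 are carried in, comorbidity is detected less completely before the pandemic than during it, which biases the comorbidity-adjusted RR of secondary objective 2 downward

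*Protocol*

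**What the plan says.** - Section 4.6.3: comorbidities enter as known HZ risk factors ("Comorbidities that have been identified as risk indicators for HZ will be considered for the analysis"). A subject is taken to "have a given condition from the first appearance of the comorbidity-related diagnosis date until the end of the follow-up period". No look-back window is set, and a condition never lapses.
- Section 4.8: the Annex 1 variables, which include the ambulatory (SIA) and hospital (MBDS) comorbidity codes, are requested "for the period from July 2017 until at least December 31st 2020".
- Annex 1, section 3.1, gives another period for the same variables: "for the period from 1 January 2007 to 31 January 2015 for subjects". It ends almost three years before follow-up can begin.
- Section 4.2: follow-up starts at the "latest of start of the study (1st January 2018), first date of registration in the database or date of the 18th birthday".
- Section 4.5.1: "Pre-pandemic period will be considered from January 1st 2018 to March 14th 2020". The pandemic period runs from that date to the end of the study.
- Section 4.9.9, item 2: the pandemic period is compared with the pre-pandemic period by Poisson or negative binomial regression. "Age, sex and comorbidities will be considered for the adjustment".
- Section 4.9.8: HZ rates are also described by comorbidity, for the pre-pandemic period and within the pandemic period.

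**The concern.** July 2017 is six months before follow-up starts. That matches the HZ-free interval required by the case definition in section 4.3, but it is short for establishing who already has a chronic disease. Short history alone would mainly weaken the adjustment. The difficulty here is that the length of history differs between the two periods that objective 2 compares, because it grows with calendar time for everyone.

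A comorbid subject whose condition has not yet been coded in the extract counts as having none. Such subjects raise the HZ rate of the no-comorbidity group, and there are more of them early than late. Within that group the rate therefore falls from the first period to the second with no real change, and adjustment passes the fall on to the pandemic RR. The unadjusted RR is untouched. At stake is a modest true increase being masked, or a null result being reported as a reduction. The comorbidity-specific rates of the two periods would not be comparable for the same reason.

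**Working it through.** The protocol gives no figure for look-back or for the precision of objective 2. Its one power figure (0.760864, section 4.9.5) concerns the primary comparison. It reproduces at 0.762 with a two-proportion calculation, and nothing below depends on it.

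**Look-back.** Assume the request starts on 1 July 2017 and earlier diagnoses are not supplied. History available to a continuously registered subject:
- 1 January 2018: 0.50 years
- 14 March 2020: 2.70 years
- 31 December 2020: 3.50 years
- Mean, pre-pandemic: (0.50 + 2.70)/2 = 1.60 years over a period of 2.20 years
- Mean, pandemic: (2.70 + 3.50)/2 = 3.10 years over a period of 0.80 years

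The request runs to at least 31 December 2020, so 3.50 is a minimum.

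**Bias model.** Assumed, not in the protocol: true prevalence p (30, 40, 50%), HZ rate ratio for comorbidity R (1.3, 1.5, 2.0), first coding of a prevalent condition at rate λ (0.25, 0.5, 1, 2 per year), and no false-positive codes. The true period RR is set to 1.
- Detected share S in a period from look-back a to b: S = 1 − [exp(−λa) − exp(−λb)] / [λ(b − a)].
- Relative HZ rate in the no-recorded-comorbidity group: [(1 − p) + p(1 − S)R] / (1 − pS).
- In the recorded group the rate is R in both periods.
- The two groups are combined by the Mantel-Haenszel rate ratio.

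**Central case (p = 50%, R = 1.5, λ = 0.5).**
- S = 0.528 pre-pandemic and 0.787 pandemic.
- No-comorbidity rate: (0.5 + 0.5 × 0.472 × 1.5)/(1 − 0.264) = 1.160 pre-pandemic; (0.5 + 0.5 × 0.213 × 1.5)/(1 − 0.393) = 1.088 pandemic. Ratio 0.938.
- Recorded-comorbidity ratio: 1.
- Person-time (pre-pandemic, pandemic), per subject: 1.6176 and 0.4850 without recorded comorbidity; 0.5809 and 0.3144 with. Relative events: 1.8768 and 0.5277; 0.8713 and 0.4716.
- Mantel-Haenszel numerator: 0.5277 × 1.6176/2.1026 + 0.4716 × 0.5809/0.8953 = 0.712. Denominator: 1.8768 × 0.4850/2.1026 + 0.8713 × 0.3144/0.8953 = 0.739. Adjusted RR = 0.963.

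**Whole grid.** The null adjusted RR runs from 0.940 to 0.994, a bias of 0.6% to 6%. A separate expected-count Poisson regression (prevalence 20-50%, rate ratio 1.2-2.0, coding 0.3-1.5 per year) gave 0.939 to 0.995. It gave 1.000 unadjusted, and 1.000 when comorbidity carries no HZ risk.

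**Precision.** With 4 million subjects (section 4.9.1) and 5.02 per 1000 person-years (section 4.9.2), expected events are 4,000,000 × 0.00502 × 2.198 = about 44,146 and 4,000,000 × 0.00502 × 0.799 = about 16,053. The 95% CI half-width is exp[1.96 × √(1/44,146 + 1/16,053)] − 1 = 1.8%. In 25 of the 36 grid scenarios the null RR lies more than 1.8% below 1.

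**What shrinks the bias.**
- A share c of prevalent conditions already known at the start, so that S becomes c + (1 − c)S. In the central case the RR is 0.979 at c = 50%, 0.991 at 80% and 0.995 at 90%.
- Faster coding: over the same p and R, the bias is 0.3-1.1% at 3 per year and 0.1-0.5% at 4 per year.

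**The case against.** The strongest reply is that section 4.6.3 refers to the date of the diagnosis and not to the first code in the extract, and that Annex 1 lists activation and deactivation dates from the SIA morbidity database separately from visit records. If conditions still active in July 2017 come with their original activation dates, most chronic disease is known on 1 January 2018 and the bias largely goes. This stands as a condition on the finding. The protocol does not say that earlier activations are returned, and section 4.8 read as written limits the request to July 2017 onward.

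The Annex 1 period might be read as supplying the earlier history. It cannot do so as it stands: it ends in January 2015, and the protocol nowhere says that the two periods are to be combined. It does mean that July 2017 is not settled, and the two sections must be reconciled.

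It is also fair that prevalence, rate ratio and coding speed are all assumed, and that the 1.8% half-width is pure Poisson; the negative binomial option in section 4.9.9 would widen it. A reader might infer that objective 2 is bound to show a spurious, significant reduction. The protocol does not support that: 11 of the 36 scenarios fall within 1.8% of 1, and fast coding or carried-in diagnoses would make the bias small.

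That the SAP might deal with this is a weaker reply. The SAP can change the adjustment, but it cannot recover codes that were never requested.

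**Conclusion.** The concern holds conditionally. If diagnoses activated before July 2017 are not supplied, the protocol's own dates give 1.6 against 3.1 years of mean history, and the comorbidity-adjusted RR of objective 2 is biased downward. The direction needs only that comorbidity raises HZ risk, which is the protocol's premise, and that recorded conditions are real. The size, about 0.6-6% on the stated assumptions, is small in absolute terms but can be comparable to or larger than the sampling error of about 1.8%. It falls to about 1% or less with coding at 3 per year or faster, or in the central case with 80% or more of prevalent conditions carried in.

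A reader might extend this to the primary result. That does not follow: the SARS-CoV-2-free and laboratory-confirmed groups are compared within the pandemic period, where history runs only from 2.7 to 3.5 years. The point concerns secondary objective 2 and the comorbidity-specific rates of section 4.9.8. It should be corrected, but it does not undermine the study's main comparison.

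**What to change.** 1. In section 4.8 and Annex 1, reconcile the two request periods.
2. Start the SIA and MBDS comorbidity diagnosis request several years before 1 January 2018, and state that earlier diagnoses are supplied with their activation dates. Section 4.7 calls SIA reliable since 2007 and MBDS since 2002, so the data should exist.
3. Keep the carry-forward rule for chronic conditions.
4. Report the objective 2 RR with and without comorbidity adjustment.

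With codes back to January 2007 (10.5 more years), the Poisson regression under no true effect returns 1.000 at prevalence 35%, rate ratio 1.3 or 1.5 and coding at 0.7 per year, and 0.997 at prevalence 50%, rate ratio 2.0 and 0.3 per year.

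A fixed rolling window would also equalise history, but lasting conditions would lapse without a recent code. A six-month window would detect only 1 − exp(−0.5 × 0.5) = 22% of comorbid subjects at 0.5 per year, so the earlier request is preferable.

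The cost is a larger data extract and a few lines of protocol text. The change has to be made before extraction.
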